5.1 ENTRY CRITERIA

5.1.1 Inclusion Criteria

Subjects must meet all of the following criteria:

1. ≥ 18 years of age
2. Diagnosis of active CLL or SLL that meets at least one of the IWCLL 2008 criteria for requiring treatment (Binet Stage \geq B and/or Rai Stage \geq I)
3. Disease that has progressed during or relapsed after at least one previous CLL/SLL therapy
4. Not appropriate for treatment with a purine-based analogue regimen (per NCCN or European Society for Medical Oncology [ESMO] guidelines), including relapse \leq 36 months from a purine-based chemoimmunotherapy regimen or relapse \leq 24 months from a purine-based monotherapy regimen
5. A cytogenetics or FISH analysis of the leukemic cells within 24 months of randomization is required to document the presence or absence of del(17p). Note: if a sample from within 24 months is not available, it should be evaluated as part of the screening laboratory evaluation to inform stratification
6. Measurable disease with a lymph node or tumor mass > 1.5 cm in at least one dimension as assessed by computed tomography (CT)
7. Eastern Cooperative Oncology Group (ECOG) performance status of 0 to 2 (corresponds to Karnofsky Performance Status [KPS] \geq 60%)
8. Willingness by subject to be randomized to receive either ofatumumab or duvelisib at the dose and schedule defined in the protocol
9. Must meet the following laboratory parameters:
 - Serum aspartate transaminase (AST/SGOT) or alanine transaminase (ALT/SGPT) ≤ 3 x upper limit of normal (ULN)
 - Total bilirubin ≤ 1.5 x ULN
 - Serum creatinine ≤ 2.0 x ULN
 - Hemoglobin ≥ 8.0 g/dL with or without transfusion support
 - Platelet count $\geq 10,000$ μ L with or without transfusion support

10. For women of childbearing potential (WCBP): negative serum β -human chorionic gonadotropin (β hCG) pregnancy test within 1 week before randomization (WCBP defined as a sexually mature woman who has not undergone surgical sterilization or who has not been naturally post-menopausal for at least 24 consecutive months [women \leq 55 years] or 12 consecutive months [women $>$ 55 years])
11. Willingness of male and female subjects who are not surgically sterile or postmenopausal to use medically acceptable methods of birth control from the first dose of study drug to 30 days after the last dose of duvelisib and for 12 months after last dose of ofatumumab. Sexually active men, and women using oral contraceptive pills, should also use barrier contraception

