6.3.9.2 Investigator assessment of response and progression status

Assessment of response and progression status will be evaluated by the investigator for clinical decision-making using criteria derived from the IWCLL response criteria for subjects with CLL ([Table 11](#)) and IWG response criteria for subjects with SLL ([Table 12](#)).

The CLL/SLL response definitions for this protocol (provided below) include modifications to the IWCLL/IWG response criteria related to PD based on the understanding that agents like duvelisib, which target the B-cell receptor signaling pathway, can mobilize CLL/SLL cells from tissues into the peripheral blood²³ interfering with their homing.^{24,25} Specifically, two modifications have been made: (1) an additional category has been added to allow for PR with lymphocytosis (PRwL); and (2) the criteria for PD do not include PD based only on worsening lymphocytosis or isolated increase in target lesion(s) in the absence of other objective evidence of disease progression.

Table 11: CLL Response Criteria (modified from IWCLL) ^{1, 22}

Variable	Complete Response (CR)	Partial Response (PR)	Progressive Disease (PD)
GROUP A			
Lymphadenopathy (CT scan)	None > 1.5 cm	Decrease \geq 50%	New lesions (> 1.5 cm) or increase \geq 50% in diameter of any single lesion or the SPD ^a
Hepatomegaly (CT scan) ^b	None	Decrease \geq 50% or normal	Increase \geq 50% of previously noted or de novo appearance ^a
Splenomegaly (CT scan) ^b	None	Decrease \geq 50% or normal	Increase \geq 50% of previously noted or de novo appearance ^a
Blood lymphocytes	< 4000/ μ L	Decrease \geq 50% from baseline or < 4,000/ μ L	Increase \geq 50% over baseline or nadir (whichever is lowest) and \geq 5,000 per μ L
Marrow ^c	Normocellular, < 30% lymphocytes, no B-lymphoid nodules. Hypocellular defines CRi in CLL subjects only	If performed: 50% reduction in marrow infiltrate, or presence of B-lymphoid nodules	
GROUP B			
Platelet count without transfusions or growth factors	> 100,000/ μ L	> 100,000/ μ L or increase \geq 50% over baseline	Decrease of \geq 50% from baseline secondary to CLL
Hemoglobin without transfusions or growth factors	> 11.0 g/dL	> 11.0 g/dL or increase \geq 50% over baseline	Decrease of > 2 g/dL from baseline secondary to CLL
Neutrophils without growth factors	> 1500/ μ L	> 1500/ μ L or \geq 50% improvement over baseline	

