Note: **Group A** criteria define tumor load; **Group B** criteria define the function of the hematopoietic system (or marrow) SPD = Sum of the products of multiple lymph nodes (as evaluated by CT scans). Use of Positron Emission Tomography (PET) imaging is not indicated in CLL/SLL.

- Disease progression confirmed by CT scan is required in the setting of PE findings without other Group A criteria or worsening disease-related constitutional symptoms/cytopenia(s).
- PE is the minimum requirement to meet criteria for PR or SD; CT scan is required for determination of response to confirm CR/CRi (CLL subjects only) or if PE is inconclusive.
- Bone marrow parameters may be irrelevant in the setting of some response categories.

Complete Response/Remission (CR): all of the criteria have been met, and subjects have no disease-related constitutional symptoms

Partial Response/Remission (PR): at least two of Group A criteria plus one Group B criteria have to be met. For subjects with lymphadenopathy at baseline as the only abnormal Group A criteria (eg. no organomegaly, blood lymphocyte count < 4,000/ μ L, and negative bone marrow), all Group A criteria plus one Group B criteria have to be met.

PR with Lymphocytosis (PRwL): For subjects with lymphadenopathy at baseline as the only abnormal **Group A** criteria (eg. no organomegaly, blood lymphocyte count < 4,000/ μ L, and negative bone marrow) who have a $\geq 50\%$ reduction in lymphadenopathy plus one **Group B** criteria but with isolated progressive lymphocytosis (blood lymphocyte count $\geq 4,000/\mu$ L).

Stable Disease (SD): absence of PD and failure to achieve at least a PR/PRwL

Progressive Disease (PD): appearance of any new lesions or at least one of the **Group A** or **Group B** criteria met with the following exceptions:

- Due to the pharmacologic property of duvelisib to mobilize CLL cells from tissues into the peripheral blood, isolated lymphocytosis should not be considered progressive disease in the setting of other indications of response such as reduced lymph node size or organomegaly or improvement in hemoglobin/platelets²²

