## 6.3 Multiple Comparisons/Multiplicity Adjustment

Of the secondary endpoints, ORR and OS are designated as key secondary efficacy endpoints. The primary endpoint and key secondary endpoints will be tested at an overall one-sided alpha level of 0.025 based on a gatekeeping approach.

If the primary endpoint is significant, the two key secondary endpoints will be sequentially tested in the order listed above. ORR will be tested at the one-sided 0.025 level only if PFS is declared statistically significant. OS will be tested according to the planned alpha spending specified in [Section 3.5.2](#) only if PFS and ORR are declared statistically significant. If any null hypothesis is not rejected in this sequence of tests, formal sequential testing will be stopped.

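### As written, Table 11 lets Group A items that were normal at baseline count toward a CLL partial response, so a subject with no improvement can be a responder in the formally tested ORR.

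*Protocol*

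**What the plan says.** Table 11 in Protocol Section 6.3.9.2 lists five Group A items (nodes, liver, spleen, blood lymphocytes, marrow) and three Group B items (platelets, hemoglobin, neutrophils). The general PR rule is "at least two of Group A criteria plus one Group B criteria have to be met".

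The PR cells read as follows:
- Liver and spleen: "Decrease \geq 50% or normal".
- Blood lymphocytes: a fall of at least "50% from baseline or < 4,000" per microlitre.
- Group B, for example hemoglobin: "> 11.0 g/dL or increase" by at least half. The absolute level alone is enough.
- Marrow: assessed only if the procedure is done.

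There is one exception. "For subjects with lymphadenopathy at baseline as the only abnormal Group A criteria", the rule becomes "all Group A criteria plus one Group B criteria have to be met". PRwL is confined to that same nodes-only group, with lymphocytes below 4,000 and a negative marrow at baseline.

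Protocol Section 6.3.9.3 has the independent panel use the Table 11 criteria. SAP V4.0 Section 7.2.2.1 counts CR, CRi, PR or PRwL at the best single time point as response. On testing, SAP Section 6.3 says "ORR will be tested at the one-sided 0.025 level only if PFS is declared statistically significant", and OS is tested only if PFS and ORR are both significant.

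**The concern.** A response should record improvement. Here two of the required items can be satisfied by organs that were never enlarged, and the Group B requirement by a blood count that was never low. A subject can then meet PR at screening and still meet it at Cycle 3 with nothing changed.

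The nodes-only exception blocks this for subjects whose sole Group A abnormality is lymphadenopathy. It does not apply once lymphocytes or marrow are also abnormal. Inclusion criterion 6 gives every subject nodal or mass disease ("Measurable disease with a lymph node or tumor mass > 1.5 cm in at least one dimension"), and Protocol Section 1.2.1 describes CLL as also involving marrow and blood. The usual CLL subject therefore falls outside the safeguard.

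ORR is the first key secondary endpoint and the gate to OS. DOR and TTR both depend on the date of first response, so a zero-change PR at the first assessment would date a response that did not occur.

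**Working it through.** The documents give no design rate or power for ORR, so there is no planned figure to reproduce. The check is a reading of the rule, followed by an illustration on stated assumptions.

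**Step 1: one profile.** Take a CLL subject with enlarged nodes, lymphocytes above 4,000, normal liver and spleen, and hemoglobin above 11 g/dL, with no change on treatment.
- Nodes: no 50% decrease, not met.
- Lymphocytes: neither halved nor below 4,000, not met.
- Liver normal: met. Spleen normal: met. Group A total = 2.
- Hemoglobin above threshold: Group B total = 1.

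The result is PR. Stable disease cannot override it, because SD requires that PR/PRwL was not reached. Unchanged findings do not meet PD.

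**Step 2: all zero-change profiles.** Nodes are abnormal and unchanged, one Group B item is above threshold, and marrow is not repeated. Liver, spleen, lymphocytes and marrow can each be normal or abnormal at baseline, giving 2 × 2 × 2 × 2 = 16 profiles. The Group A items met are those normal among liver, spleen and lymphocytes.

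| Normal among liver, spleen, lymphocytes | Profiles | PR as written |
|---|---|---|
| 3, marrow negative (nodes-only exception) | 1 | 0 |
| 3, marrow positive | 1 | 1 |
| 2 | 6 | 6 |
| 1 | 6 | 0 |
| 0 | 2 | 0 |
| Total | 16 | 7 |

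If only items abnormal at baseline may count, 0 of 16 are PR. These are counts of logical profiles, not frequencies of subjects.

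**Step 3: a second route.** One normal organ plus a nodal fall of at least 50% makes two Group A items, whatever the lymphocyte count. A subject with baseline lymphocytosis who responds in the nodes while lymphocytes persist or rise is then PR, not PRwL. The ORR analyses without PRwL (SAP Section 7.2.2.1) would leave that subject in.

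**Step 4: whether planned analyses would reveal it.** Investigator ORR, confirmed ORR and ORR without PRwL all reuse the same PR rule. A static PR at Cycle 3 is still present at Cycle 5, nominally 2 × 28 = 56 days later, so it passes the 8-week confirmation. Lymph node response rate would show the discrepancy, but SAP Section 7.2.2 claims no significance for it.

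**Step 5: effect on the ORR comparison.** Suppose true response rates are p1 and p2, and a share q of non-responders in each arm meets PR trivially. Observed ORR in an arm is p + q(1 − p), so the difference becomes (1 − q)(p1 − p2). All inputs below are assumptions. Duvelisib is set at 17/30 = 56.7%, borrowed as a starting value from the ≤ 25 mg group in Protocol Section 1.3.2.2; it is CR + PR only, so it is not this trial's expected ORR. The ofatumumab rate and q are not in the documents. Power uses the normal approximation for two proportions, 150 per arm, one-sided 0.025, unstratified.

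| Ofatumumab ORR | q = 0 | q = 0.25 | q = 0.5 |
|---|---|---|---|
| 20% | 36.7 points, power 1.00 | 27.5 points, 0.998 | 18.3 points, 0.93 |
| 35% | 21.7 points, 0.97 | 16.3 points, 0.82 | 10.8 points, 0.56 |
| 45% | 11.7 points, 0.53 | 8.8 points, 0.35 | 5.8 points, 0.22 |

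For example, at 35% and q = 0.25: 56.7 + 0.25 × 43.3 = 67.5, and 35 + 0.25 × 65 = 51.25, a difference of about 16.3.

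**The case against.** The best defence is operational. The rows are titled hepatomegaly and splenomegaly, so their PR cells can be read as improvement of an existing abnormality, and expert reviewers working from IWCLL-derived criteria might apply them that way. The nodes-only exception tells against this reading. It requires every Group A item to be met in subjects whose other Group A items were normal from the start, which is possible only if a normal item counts as met. A review charter may contain a baseline rule, but neither document states one.

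The second defence is that little is at risk. This stands in part. The rule is the same in both arms, and zero-change PRs do not by themselves inflate type I error. PFS rests on a separate PD definition. SLL subjects use Table 12, which has its own nodal criterion.

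A reader might try to size the effect by moving the stable-disease subjects of the protocol's Table 7 into PR. The documents do not support that. The table's footnote says SD there includes PR with lymphocytosis, part of which this trial already counts as response. Section 1.5, at an earlier cut, reports that 11 of 13 SD subjects at ≤ 25 mg had a nodal response, so they were not mainly unchanged.

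A reader might also infer that restricting PR to items abnormal at baseline is enough on its own. It is not. With PRwL limited to nodes-only subjects, a subject with baseline lymphocytosis, a nodal response and persisting lymphocytosis would become SD. Section 6.3.9.2 attributes such lymphocytosis to agents like duvelisib, so that loss would fall mainly on one arm.

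**Conclusion.** The CLL partial-response definition is wrong as written. It admits subjects with no improvement into ORR, a formally tested endpoint that gates OS, and into DOR and TTR. This follows from the text of Table 11 without any assumption.

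The size is not known, because the documents do not say how many CLL subjects have normal organs and an adequate blood count at baseline. The net direction is also uncertain. Zero-change PRs raise ORR in both arms and tend to shrink the difference. Nodal falls with lymphocytosis classed as PR could favour duvelisib and defeat the sensitivity analysis without PRwL. The dilution figures rest on assumed response rates, on an equal q in both arms, and on treating all 150 subjects per arm as exposed; SLL subjects are not, so a given q among CLL subjects has less effect overall. A claim that the rule biases the trial toward a false positive would go beyond the documents.

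**What to change.** Amend Table 11 and the independent review criteria together, making two linked changes.

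1. PR in CLL: a Group A item counts only if it was abnormal at baseline. At least two such items must meet the PR criterion, or the single item if only one was abnormal. Items normal at baseline must stay normal. The requirement for one Group B item is unchanged.

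2. PRwL in CLL: extend it to subjects with lymphocytosis or marrow involvement at baseline who have a nodal reduction of at least 50% plus one Group B item, and whose only unmet blood criterion is lymphocytosis. They stay responders under the ORR definition but are counted as PRwL, which restores the meaning of the analyses without PRwL. The text should also say how to classify a subject with an enlarged organ but normal lymphocytes and marrow at baseline whose lymphocytes then rise. Otherwise that subject could fall between the two categories.

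If the reviewers already apply a baseline rule, the protocol should state it so that ORR can be reproduced. The cost is a few sentences and a consistent re-derivation of response, with no new data collection. ORR may be somewhat lower than under the literal rule, and some literal PRs will move to PRwL.

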6.3.9.3 Independent assessment of response and progression status

Disease progression and response for the primary and secondary endpoints will be evaluated by an independent panel of radiologists and oncologists using criteria derived from the IWCLL criteria (Table 11) for CLL subjects and the revised IWG criteria (Table 12) for SLL subjects. All disease response assessment data, including peripheral blood, physical exam, disease-related constitutional symptoms, and CT scans will be utilized in determining response and disease progression. Central review of imaging will be utilized to confirm investigator-assessed PD at the time of PD determination up to the time of the final analysis.

6.4 EARLY TREATMENT TERMINATION OF DUVELISIB OR OFATUMUMAB

If at any time during treatment with study drug (duvelisib or ofatumumab) a subject has an AE resulting in permanent discontinuation of study treatment, PD, initiates new anticancer therapy, or withdraws consent, then the assessments outlined below will be performed within 7 days of study treatment discontinuation or the decision to discontinue study treatment. ETT assessments include:

If performed within previous 14 days, do not need to be repeated:

- Urine or serum pregnancy tests will be collected from all women of childbearing potential (WCBP)
- Concomitant Medications and Procedures collection
- AE and SAE assessment
- Blood chemistry
- Liver function tests
- Biomarker assessments

If performed within previous 30 days, do not need to be repeated:

- Disease response assessments:
 - Focused physical exam /constitutional symptoms
 - Bone marrow biopsy/aspirate (if indicated)
 - Hematology
 - Blood sample for MRD
 - ECOG
 - CT scan
 - Quality of life (QoL) EQ-5D and FACIT-F

6.5 POST-TREATMENT PERIOD

6.5.1 Safety Follow-up Visit (30 Days Post-Treatment)

6.5.1.1 *Duvelisib*

For subjects randomized to duvelisib, a visit should occur 30+7 days after discontinuation or last dose of duvelisib as outlined in [Table 2](#). If possible, this visit should be conducted prior to initiation of any subsequent therapy. This visit may be a conducted as a phone screen as long as the study subject does not require laboratory and/or other assessments related to any new or ongoing AEs, in which case a clinical visit will be required. Assessments should include:

- AEs/SAEs collection
- Concomitant medications and procedures collection

Following the last dose of duvelisib, subjects will continue follow-up as described in [Table 2](#) and [Table 5](#).

6.5.1.2 *Ofatumumab*

For subjects randomized to ofatumumab, a visit should occur 30+7 days after discontinuation or last administration of ofatumumab. If possible, this visit should be conducted prior to initiation of any subsequent therapy. This visit may be a conducted as a phone screen as long as the study subject does not require laboratory and/or other assessments related to any new or ongoing AEs, in which case a clinical visit will be required. Assessments include:

- AEs/SAEs collection
- Concomitant medications

Following the last dose of ofatumumab, subjects will continue follow-up as described in [Table 4](#) and [Table 5](#).

6.5.2 Clinical Assessment Period

6.5.2.1 *Duvelisib*

Subjects who come off treatment with duvelisib prior to Cycle 19 Day 1 for reasons other than PD will continue clinic visits every other month through Cycle 19 Day 1. During this period, subjects will not receive any additional anticancer therapy (including duvelisib).

Assessments are outlined in [Table 2](#) and [Table 5](#).

Note: If a subject experiences PD within this period, then that subject may be offered ofatumumab treatment as part of another study (Study IPI-145-12) to evaluate the safety and efficacy of ofatumumab therapy after duvelisib therapy.

All subjects will be followed every 6 months for survival for up to 6 years from randomization.

6.5.2.2 Ofatumumab

Subjects who complete treatment with ofatumumab (Cycle 7) or come off for reasons other than PD will enter a Clinical Assessment Period through Cycle 19 Day 1. During this period, clinical visits will occur every other (odd) month and subjects will not receive any additional anticancer therapy (including ofatumumab).

Assessments in the Clinical Assessment Period are outlined in [Table 4](#) and [Table 5](#).

Note: If a subject experiences PD within this period, then that subject may be offered duvelisib treatment as part of another study to evaluate the safety and efficacy of duvelisib therapy after ofatumumab therapy.

All subjects will be followed every 6 months for survival for up to 6 years from randomization.

6.5.3 Follow-up

6.5.3.1 Disease Follow-up

Subjects who discontinue treatment with duvelisib or ofatumumab early (ie, ETT) due to reasons other than PD will continue to undergo disease response assessments up until Cycle 19 Day 1 (ie, Cycles 5, 7, 11, 15 and 19) or until disease progression, subject withdrawal, or initiation of additional anticancer therapy. After Cycle 19 Day 1, all subjects without progressive disease will enter Disease Follow-up. CBC and differential count will be performed approximately 3 months after the last assessment, and every 3 months thereafter until disease progression, subject withdrawal, or initiation of additional anticancer therapy. All other disease assessments should occur approximately 6 months after the Cycle 19 Day 1 Disease Response Assessment, and every 6 months thereafter until disease progression, subject withdrawal, or initiation of additional anticancer therapy. The following assessments should be performed as outlined in [Table 5](#).

Every 3 months

- CBC and differential count

Every 6 months

- CT scans of chest, abdomen and pelvis
- Bone marrow biopsy and/or bone marrow aspiration (when clinically indicated)
- Blood sample for assessment for minimum residual disease (MRD) in subjects with documented CR or CRi
- Focused physical examination, ECOG performance status, and disease-related constitutional symptoms

6.5.3.2 Survival Follow-up

For all subjects, survival follow-up will occur every 6 months for up to 6 years after randomization or until death. The first follow-up should occur 6 months (± 4 weeks) from documentation of PD or treatment discontinuation. For both duvelisib and ofatumumab-treated subjects, information on initiation of other anticancer therapy will also be collected at

each survival follow-up; these assessments may be collected through a telephone interview. Please see [Table 5](#) for more details on the follow-up assessments.

6.6 MISSED VISITS

If a subject misses a scheduled visit, the subject will continue on the protocol and attend the next scheduled visit. If a subject misses 2 scheduled visits, then the subject's continued participation in the study must be re-evaluated (see [Section 4.3](#) and [Section 4.4](#)).

